13.6.2 Critical use error - Clinically significant under-dosing

With regard to the hazard associated with under-dosing, only substantial variations in dose delivery to the lung present potential for harm to the user ([Molimard et al 2003](#), [Newman et al 2005](#)).

Following this approach, in the case of TOBI Podhaler:

- Sub-optimal techniques that will not significantly negatively impact on therapeutic outcome are not critical use errors. For example, failure to exhale fully prior to inhaling through the Podhaler device is not a critical use error.
- Occasional single instances of no powder being delivered to the lung from a capsule, as a result of a task performance error (e.g. physical slip or memory lapse) are not critical use errors. For example, a single instance of forgetting to pierce a capsule is not a critical use error.
 - This would be true for any capsule-based dry powder inhalation system, except for one that delivers an acute ‘rescue’ medication where failure to deliver a single dose could have immediate clinically significant consequences.
 - In the case of TOBI Podhaler, the impact of occasional instances of powder delivery errors is further reduced because each dose requires four capsules to be used. An error on a single capsule therefore affects only a quarter of a dose of powder.
- Difficulties or task failures that the user is aware of are not critical use errors. For example, difficulty removing TOBI Podhaler capsules from blister cards is not a critical use error. The user will be aware that they have not administered a dose and can seek assistance from their physician or nurse. They will address, rather than repeat, the task failure.

Critical use errors with the potential to result in clinically significant under-dosing all require routine repetition.

[Table 13-2](#) lists the critical use errors that could lead to the potential for clinically significant under-dosing that the user remains unaware of. For a comprehensive list with discussion of the criticality of all use steps refer to [Appendix 5](#).

Table 13-2 Critical use errors relating to clinically significant under-dosing

Aspect of Use	Description of critical use error	IFU Content
Capsule Piercing	Routine failure to adequately pierce capsules.	Step 9
	Routine failure to release blue button before inhalation.	Step 9
	Routine multiple piercing of capsules	Step 9

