Inhalation	Routine instances of exhalation into the mouthpiece after loading and before inhalation.	Step 10
	Routine instances of inadequate seal of mouth around mouthpiece.	Step 11
	Routine failure to inhale deeply (inadequate inhalation technique).	Step 12
Dosage Regime	Routine failure to administer four capsules per dose.	Step 18
	Routine failure to administer two doses per day.	General Notes/ Warnings

Aspect of Use	Description of critical use error	IFU Content
General	Routine instances of swallowing capsules, as opposed to inhalation of capsule contents.	General Notes/Warnings
	Sustained failure to dispose of a Podhaler device after it has been used for one week.	General Notes/Warnings
	Failure to identify malfunctioning Podhaler device and use reserve inhaler	General Notes/Warnings and Step 17
	Repeated washing of Podhaler leaving device damp	Step 21

Note that for the purposes of this single assessment study, it will not be possible to establish through observation whether errors would be repeated in general use. All errors with associated criticality will therefore be recorded, their root cause established in post-dose discussion where possible, and fully reported.

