13.11 Data Collection and Interpretation of Results

The objective of the HF study is to evaluate whether the user interface of TOBI Podhaler can support safe and effective use for patients with CF

Assessment against this objective will be based on:

- recording all use errors and close calls associated with the simulated inhalation of one dose of TOBI Podhaler (i.e., inhaling the contents of four placebo capsules via the Podhaler device) by subjects (CF patients and/or their caregivers. This evidence will include:
 - direct observation of use errors and close calls
 - inadequately emptied capsules identified in post-use inspection by the HF Interviewer.
- 1. assessing the root cause of use errors and close calls and establishing those which can be attributed to a flaw in the user interface
- 2. assessing the potential consequences of any errors and, in particular, for those which could result in significant harm to the subject or other user).

In addition, subjective feedback on the user interface will be sought from all subjects and will be recorded, reported and assessed.

The criticality of use errors is noted in [Appendix 5](#). This table will be referred to during analysis and reporting of the study data.

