		Appropriate response to any powder remaining in capsule: - re-inhale if more than coating remains, replacing capsule correct way	Yes	Yes	Yes if correct performance is not observed	
This task step is desirable, but not essential.
 
Use Error: failure to correctly re-insert capsule and repeat inhalation. Avoidance of this use-error is desirable, but not essential. The instruction is a description of optimal technique which reduces the risk of any capsules remaining inadequately emptied following earlier errors or failures in steps 5 to 15 above.
 
Note however that any failure to empty a capsule will be investigated in post-dose discussion, so that the root cause of failure can be determined, and fully reported.

		-re-insert and re-pierce if it does not appear to be pierced			Yes if correct performance is not observed	
This task step is desirable, but not essential.
 
Use Error: failure to correctly re-insert, re-pierce and re-inhale. Avoidance of this use-error is desirable, but not essential. The instruction is a description of optimal technique which reduces the risk of any capsules remaining inadequately emptied following earlier errors or failures in steps 5 to 15 above.
 
Note however that any failure to empty a capsule will be investigated in post-dose discussion, so that the root cause of failure can be determined, and fully reported.

		- use reserve Podhaler device if still does not appear to be pierced	-		Yes if correct performance is not observed	
Potential for critical use error.
 
Use Error: failure to use reserve Podhaler device in cases of capsules remaining inadequately pierced after correct re-insertion and re-piercing. This use error has the potential to cause clinically significant under-dosing and is therefore critical.

18	18	Repeat Steps 5 to 17 for 3 more times until your whole dose (4 capsules) has been taken	Yes	Yes	Yes if correct performance is not observed	
Potential for critical use error
 
Use Error: failure to administer four capsules per dose. If this use error is routinely repeated it will result in clinically significant under-dosing. Repeated error is critical. Occasional error is non-critical. In this single-use assessment, a failure to administer four capsules per dose will be viewed as

Item	IFU step	Task	Assessment Method			Discussion of Task Step Criticality
			Inspection of Used Capsules	Observation of Task Performance	Questioning in post-dose discussion	

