Item	IFU step	Task	Assessment Method			Discussion of Task Step Criticality
			Inspection of Used Capsules	Observation of Task Performance	Questioning in post-dose discussion	
30	-	The reserve Podhaler device provided in the package may be used if the Podhaler device: - is wet, dirty, or broken - has been dropped - does not seem to be piercing the capsule properly	-	Yes (where a reserve Podhaler is required)	Yes if correct performance is not observed	
Potential for critical use error.
 
Use Error: use of a wet, dirty, broken or faulty Podhaler device. This use error has the potential to cause clinically significant under-dosing. Routinely repeated error is critical. Occasional error is non-critical.
 
Note that this cannot be assessed via observation in a single study session. However, comprehension of the IFU section related to use of the reserve Podhaler device was assessed in the 2412 IFU validation study and all study subjects could find and understand the information in the IFU. It is therefore not intended to re-assess comprehension in this study.

31	-	Only use the Podhaler device contained in this pack. Do not use TOBI Podhaler capsules with any other device	-	-	N/A – cannot be observed, comprehension of IFU already validated	
Following this instruction is essential, but not critical.
 
Use Error: use of capsules with a different inhaler. This initially is likely to result in impaired (partial) dose delivery to the lung, with delivery declining over time until dosing is impossible. This will be evident to the user. There are therefore no hazardous consequences following inevitably from this use error.
 
Note that this cannot be assessed via observation in a single study session. However, comprehension of the IFU section related to capsule use was assessed in the 2412 IFU validation study and all study subjects could find and understand the information in the IFU. It is therefore not intended to re-assess comprehension in this study.

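### Critical task (l), recognising a faulty inhaler and using the reserve, may yield no data, and the protocol disagrees with itself on how (l) and (m) are assessed and when a reserve-device failure is critical

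*Protocol*

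**What the plan says.** **Coverage of (l).** PMR 1928-5, reproduced in protocol Section 1.1, requires the study to include every critical task from the updated risk analysis. Section 3.2.2 and Table 13-2 both list as critical: "Failure to identify malfunctioning Podhaler device and use reserve inhaler". Section 3.2.2 then splits its list. Errors on items a to l are followed up in the post-dose discussion. Only m, n and o are set aside, on the strength of study CTBM100C2412.

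**How (l) is to be assessed.** In Appendix 5 item 30 the observation cell reads "Yes (where a reserve Podhaler is required", and the questioning cell applies if correct performance is not seen. The note beside them says that the task cannot be assessed by observation in one session, that "comprehension of the IFU section related to use of the reserve Podhaler device was assessed in the 2412 IFU validation study", and that comprehension is not to be assessed again. The Appendix 4 script tells subjects that the device is new and unused. Its post-use questions do not mention a faulty inhaler or the reserve.

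**When a failure is critical.** Item 17 describes the error as "failure to use reserve Podhaler device in cases of capsules remaining inadequately pierced after correct re-insertion and re-piercing" and concludes: "This use error has the potential to cause clinically significant under-dosing and is therefore critical". Item 30, on using a wet, dirty, broken or faulty device, says: "Routinely repeated error is critical. Occasional error is non-critical". Section 13.6.2 states: "Critical use errors with the potential to result in clinically significant under-dosing all require routine repetition". Of Appendix 5, Section 13.11 says: "This table will be referred to during analysis and reporting of the study data".

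**Task (m), two doses per day.** Section 3.2.2 says it will not be tested. Item 25 says comprehension will be re-assessed because the IFU wording changed, and Appendix 4 scripts a question on capsules per day.

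**The concern.** A validation study needs some evidence on each task it claims to validate. For (l) the evidence depends on an event that the study neither creates nor can count on: a new device failing, or being dropped or soiled, in a session that uses four capsules. If that does not happen, the only other route is a question, and item 30 does not settle whether one is asked. The protocol could then be followed in full and still give nothing on (l), overall or in an age group.

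The criticality conflict is a separate matter. Appendix 5 is the reference for classifying errors. If a subject keeps using a device that will not pierce, one row makes that single failure critical and another makes it non-critical. The study conclusion rests on judging whether critical errors occurred and why, so the label should not depend on which row the analyst opens.

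**Working it through.** **1. The plan's own figure.** 3 age groups × 15 = 45 completers (Section 9.8), which reproduces. It comes from guidance, with no power calculation, and Section 9.4.2 plans no hypothesis test.

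**2. Routes by which data on (l) could arise.**

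- Observation: only when a reserve is needed (item 30). No simulated fault appears in Section 3.2, Section 13.10 or Appendix 4.
- Scripted question: none. The nearest asks what to do if a full dose was not received. It does not ask about a faulty inhaler or the reserve.
- Conditional question (items 17 and 30): asked if correct performance is not observed. Read literally, a subject who never needs the reserve has shown no correct performance, so nearly everyone would be asked. Item 30's note points the other way, and the script has no such question.
- Interviewer discretion: Appendix 4 allows probing of errors and difficulties, but nothing requires a reserve-device probe where no fault arose.

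**3. How often observation might occur.** The documents give no malfunction or reserve-use rate. The 64 postmarketing device cases in Section 13.5.3 have no denominator. Assume that each subject independently needs a reserve with probability p. Then P(no observation in n subjects) = (1 − p)^n.

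| p (assumed) | n = 45 | one age group, n = 15 |
|---|---|---|
| 1% | 0.99^45 = 0.636 | 0.99^15 = 0.860 |
| 2% | 0.98^45 = 0.403 | 0.98^15 = 0.739 |
| 5% | 0.95^45 = 0.099 | 0.95^15 = 0.463 |

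A second illustration uses the piercing route alone. Section 13.5.1 reports failure to pierce in 1.5% of capsules, among trained users with empty capsules. The IFU sends the user to the reserve after two failed attempts on one capsule. With 45 × 4 = 180 capsules, 180 × 0.015 = 2.7 first failures are expected. Let r be the unknown chance that the second attempt also fails. Then P(any case) = 1 − (1 − 0.015r)^180, which is 4% for r = 1.5% and 93% for r = 100%. The range is too wide to settle anything: the number of observations is unknown and may be zero.

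**4. Criticality, side by side, for a device that does not pierce.**

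| Place | Repetition needed to be critical? |
|---|---|
| Section 13.6.2, general statement | Yes, for all under-dosing errors |
| Table 13-2, entry for (l) | Not stated; no 'Routine' |
| Appendix 5 item 17, reserve row | No condition given |
| Appendix 5 item 30 | Yes |

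Items 17 and 30 word the error differently: not switching, against continuing with a faulty device. Item 30 names improper piercing among its triggers, so a subject who carries on with a non-piercing device after re-insertion and re-piercing falls under both.

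**5. Task (m).** Section 3.2.2 (not tested) and item 25 (re-assessed) cannot both stand. Item 25's own cell makes the question conditional on what dosing shows, while the Appendix 4 question has no such condition.

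**The case against.** The best defence concerns item 30. The limit to cases where a reserve is needed sits in the observation cell only; the questioning cell has no such limit. Items 20 and 21 have first rows with no planned observation and the same conditional questioning, while items 26 to 29 and 31, which are meant to go unquestioned, are marked not applicable. Item 30 was not marked that way. Its note may mean only that routine repetition cannot be seen in one session, and item 24 likewise combines observation and questioning with no new comprehension test. This reading is fair, so a reader who infers that (l) certainly has contingent data only goes further than the text allows. What stands is that the note and the script do not support the generous reading either, so two sites could follow the protocol and act differently.

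It can also be said that errors are captured whatever their label. That is right: Section 13.6.2 has all errors with associated criticality recorded, investigated where possible and fully reported.

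Two stronger inferences are tempting. One is that zero errors on (l) would be presented as 45 successes. The documents do not show this. Steps are marked pass or fail, errors are listed by participant, the SAP leaves human factors analysis out of scope, and neither the checklist form nor the vendor's analysis plan is among the documents. The other is that the reserve-inhaler wording changed after study 2412 and goes unvalidated. Nothing says it changed, and item 30 does not flag new wording as item 25 does.

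**Conclusion.** The point holds in two parts. First, the plan does not secure any data on (l), although it lists (l) as critical, keeps it among the tasks examined here, and answers a requirement that covers all critical tasks. The size of the gap cannot be computed from the documents. The 64% to 10% chance of no observation in 45 rests entirely on an assumed 1% to 5% need for a reserve and on independence between subjects. Second, the text conflicts as written: items 17 and 30 on when a reserve-device failure with a non-piercing device is critical, Section 13.6.2 against its own Table 13-2 entry, and Section 3.2.2 against item 25 and Appendix 4 on (m). The conflict on (m) loses no data, because a related question is scripted. The consequences are for coverage of (l) and for how a failure is classified, not for whether it is recorded. This should be changed, but it does not undermine the rest of the study.

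**What to change.** 1. Add one question to Appendix 4, asked of every subject or pair after the open questions, for example: *How would you know if the inhaler was not working properly, and what would you do then?* Record whether the reserve inhaler and the item 30 triggers are named. Do not prompt for those left out, since the guide asks the interviewer not to prompt or lead. Set the scoring in Appendix 5 beforehand, and report the answers as comprehension that supplements observed use.
2. Report observed reserve-device use and errors over the number of subjects who had the opportunity, and say so plainly if that number is zero.
3. Reconcile Section 3.2.2, Section 13.6.2 with Table 13-2, and Appendix 5 items 17, 25 and 30 on how (l) and (m) are assessed and when a reserve-device failure counts as critical. The choice of rule belongs to the sponsor; this review proposes none.

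The cost is a few minutes in a session of about 60 minutes, a checklist edit and one reporting rule. The question shows comprehension only. It does not show that a user would notice a fault during use.

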WHO	World Health Organization

1 Introduction

This study is a human factors validation study to validate the user interface of TOBI Podhaler by establishing that the product can support safe and effective use for the intended users.

The study is being conducted to fulfill US FDA post-marketing requirement (PMR) 1928-5:

Conduct a human factors validation study to demonstrate that the user interface of the product can support safe and effective use for the intended users. The human factors validation study should be conducted in patients aged 6 years and older under simulated yet representative of realistic use conditions and include all the critical tasks identified from your updated use-related risk analysis.

In addition to Human Factor (HF) assessments, limited clinical data (e.g., patient demographics, AEs, SAEs, vital signs, medical history and concomitant medications) will be collected.

NOTE: this document describes the summaries on clinical safety data only, i.e., the data collected on Mylan eCRFs. The HF data will not be entered into Mylan database and HF analysis is out of scope of this document.

[figure not shown]
1.1 Study design

This is an open-label, non-randomized, single placebo arm, single visit HF study.

The study will enroll 50 cystic fibrosis (CF) subjects with the aim of having 45 subjects completing the study across three age groups of approximately 15 subjects each (6-10 years, 11-17 years, and ≥ 18 years). Only CF patients who are naïve to the use of the Podhaler device will be enrolled. Patients will take a four-capsule dose from the Podhaler device using placebo capsules (powder-filled) at the visit. The study requires that any caregiver is also naïve to the use of the Podhaler device.

These patients and caregivers will not be trained prior to using TOBI Podhaler and will be observed during the dosing procedure and interviewed afterwards to establish root cause of any errors during the inhalation process.

Figure 1-1 Study design

1.2 Study objectives and endpoints

The objective of this study is to evaluate whether the user interface of TOBI Podhaler can support safe and effective use for patients with CF by assessing use errors and close calls associated with the simulated inhalation of one dose (4 capsules) using the TOBI Podhaler device. HF assessments will be performed to primarily support the objective; data collection, analyses and reports on HF data will be done independently by Team Consulting, a contract research organization (CRO), and are not discussed in this document.

2 Statistical methods

The clinical data as collected on eCRFs will be reported as the supplementary information in the study report. This will be performed by ICON using SAS[®] 9.4.

Because there is only one placebo arm (and one-dose), no comparison or statistical hypothesis test is applicable to this study. All data will be summarized descriptively based on data collected in clinical database. More details will be defined in a separate document with mocked shells.

2.1 Data analysis general information

In general, categorical variables will be presented as the number and percentage of subjects in each category. Continuous variables will be summarized using descriptive statistics (number of subjects, mean, standard deviation, median, minimum, and maximum). The analysis will be based the safety set (patients who have inhaled the contents of at least one capsule of placebo).

2.2 Analysis sets

Two analysis sets are defined in the protocol:

The Screen Failure Set (SF) includes all patients who signed the informed consent and failed the screening.

The Safety set (SAF) includes all patients who entered the study and who have inhaled the contents of at least one capsule of placebo, regardless of whether the related HF assessment is completed.

NOTE: SAF set will be used for all analyses discussed in this document.

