3.7 Risks and benefits

Besides contributing to the assessment of the user interface that could be of benefit to patients, this trial may not offer a direct benefit to the subjects. Any risk to subjects in this trial will be minimized by compliance with the inclusion/exclusion criteria. No active drug is being administered but there is a potential risk of an allergic reaction from unrecognized sensitization to the placebo content (i.e. DSPC (1, 2-distearoyl-sn-glycero-3-phosphocholine) and/or calcium chloride).

As with all inhaled medications, cough and bronchospasm (asymptomatic or reported as wheeze) may occur; especially in subjects with known or suspected bronchial hyper-responsiveness.

Patients who experience any of these symptoms after dosing should be managed as per standard of care and the events should be recorded as Adverse Events (AEs).

Subjects will also be asked not to continue with any activity that they find painful. If bodily fluid is drawn or expelled, the HF Interviewer and Investigator/designated staff will quarantine the Podhaler device and anything that could have come into contact with the bodily fluid. The room will be sanitized and the subject will be treated as per the investigator decision. All AEs must be recorded on the appropriate CRF capturing AEs.

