5.6.2 Discontinuation of study treatment

Discontinuation of study treatment for a patient occurs when study drug is stopped earlier than the protocol planned duration, and can be initiated by either the patient or the investigator. In this single visit study, discontinuation will occur if the subject does not complete the inhalation of the 4 placebo capsules and/or the HF interview.

The investigator must discontinue study treatment for a given patient if, on balance, he/she believes that continuation would negatively impact the risk/benefit of trial participation. Study treatment must be discontinued under the following circumstances:

- Patient wish
- Any situation in which study participation might result in a safety risk to the patient
- Non-compliance of the subject with study procedures or investigator instructions, as per the investigator's judgment
- Emergence of Adverse Events (AE) when worsened from study entry or any newly occurring development of AEs
- Any other protocol deviation that results in a significant risk to the subject's safety

Subjects who are prematurely withdrawn from the study will be replaced by an equal number of newly enrolled subjects to meet the intended target of 15 subjects in each of the three age categories i.e., 45 completed subjects. However, premature withdrawal does not necessarily mean that the subject has failed to complete the HF assessment. It is possible in certain circumstances that subjects could demonstrate the ability to use TOBI Podhaler and carry out the dosing task without using all four capsules; for example, a 6 year-old child may not demonstrate sufficient attention or patience for the entire dose to be taken.

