8.5 Adjudication Committee

Not required.

9 Data analysis

The analysis will be conducted on all subject data at the time the trial ends. Any data analysis carried out independently by the investigator should be submitted to the Sponsor before publication or presentation.

Data collected from clinical and human factor assessments will be presented. All safety data, including AEs, SAEs, vital signs and concomitant medications will be summarized descriptively. Safety analysis will be based on descriptive statistics for subjects who have inhaled the contents of at least one capsule of placebo.

Unless otherwise specified, clinical data will be summarized as follows. Categorical variables will be presented as the number and percentage of subjects in each category. Continuous variables will be summarized using descriptive statistics (number of subjects, mean, standard deviation, median, minimum, and maximum).

For each item of the HF Assessment Checklist the number and percentage of subjects with each response will be summarized descriptively. Where relevant: number, percentage, average, standard deviation, minimum and maximum shall be presented per age group. A bar chart illustrating each response will also be displayed. A comprehensive data table will also be provided which gives details of all errors related to each task step listed by participant.

A report from the HF vendor will be prepared summarizing both objective performance data and subjective data collected. The results attained, the difficulties, deviations and/or complaints observed/reported will be reported and analyzed following completion of the study. Analysis and discussion of observations and qualitative assessment will also be presented.

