9.1 Analysis sets

The screen Failure Set: The Screen Failure Set included all patients who signed the informed consent and failed the screening.

The Safety set (SAF) will consist of all subjects that enter the study and who have inhaled the contents of at least one capsule of placebo regardless of whether the related HF assessment is completed.

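### The Safety Set's one-capsule threshold can leave out a subject who reacts and is stopped during the first capsule

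*SAP*

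**What the plan says.** **Entry rule.** SAP 2.2 states: "The Safety set (SAF) includes all patients who entered the study and who have inhaled the contents of at least one capsule of placebo". Protocol 9.1 limits the set to subjects "who have inhaled the contents of at least one capsule of placebo regardless of whether the related HF assessment is completed". The opening text of Protocol Section 9 agrees: "Safety analysis will be based on descriptive statistics for subjects who have inhaled the contents of at least one capsule of placebo". SAP 2.1 repeats the threshold.

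**Scope.** A note in SAP 2.2 adds: "SAF set will be used for all analyses discussed in this document". SAP 2.5.1 places the AE and SAE summaries on this set, and SAP 2.3 does the same for disposition, discontinuation reasons and protocol deviations. The only other population is the Screen Failure Set, which "includes all patients who signed the informed consent and failed the screening".

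**Reactions and stopping.** Protocol 3.7 warns that "cough and bronchospasm (asymptomatic or reported as wheeze) may occur" and also mentions allergic reaction. Protocol 5.6.2 includes this among the circumstances in which study treatment must be discontinued: "Emergence of Adverse Events (AE) when worsened from study entry or any newly occurring development of AEs".

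**Table trigger.** Under SAP 2.5.1, AE summary tables are produced only if five or more patients report an AE.

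**The concern.** A safety population should hold everyone exposed to the product. Here entry depends on getting through a capsule, while the reactions the protocol anticipates can occur on the first breath and are themselves listed as grounds for stopping. A subject stopped mid-capsule because of an AE may therefore fail the entry rule because of that AE. The loss falls on the earliest withdrawals due to AEs, which the AE-withdrawal summary exists to show.

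**Working it through.** **Step 1. Follow one subject through the rules.** The subject passes screening, inhales once from capsule 1, wheezes, and is stopped with powder remaining.

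- *Screen Failure Set:* no, because screening was passed.
- *Safety Set:* no, on the natural reading. Protocol 9.4 describes a full dose as inhaling the contents of four capsules, and Protocol 13.10.1 judges that goal by how far the capsules were emptied. Used consistently, the contents of one capsule means that capsule's powder, not some of it.
- *AE, AE-withdrawal and disposition tables (SAP 2.5.1, 2.3):* absent, because all are on the Safety Set.
- *AE and SAE listings (SAP 2.5.1):* absent only if the SAP 2.2 note is applied to them. Section 2.5.1 does not itself restrict them.
- *Source and CRF:* present. AEs are recorded from consent (Protocol 7.1), and SAEs go to the sponsor within 24 hours (Protocol 7.2.2).

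**Step 2. The plan's own numbers.** 3 age groups × 15 = 45 completers, which reproduces the stated figure. With 50 enrolled, implied non-completion is 1 − 45/50 = 10%; the documents do not state a rate. They give no AE rate and plan no hypothesis test, so everything below is illustration.

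**Step 3. Effect on the tabulated proportion.** Let N be the subjects who started inhaling, e those in the Safety Set with an AE, and k those excluded with an AE.

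- Reported proportion: e/(N − k)
- Proportion among all exposed: (e + k)/N
- Difference: k(N − k − e)/[N(N − k)]

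Take k = 1. N = 50 assumes all enrolled start inhaling. N = 16 stands for one age group (50/3 is about 16.7).

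| N | e | Reported | All exposed | Difference |
|---|---|---|---|---|
| 50 | 0 | 0/49 = 0.0% | 1/50 = 2.0% | 2.0 points |
| 50 | 4 | 4/49 = 8.2% | 5/50 = 10.0% | 1.8 points |
| 50 | 6 | 6/49 = 12.2% | 7/50 = 14.0% | 1.8 points |
| 16 | 0 | 0/15 = 0.0% | 1/16 = 6.3% | 6.3 points |
| 16 | 1 | 1/15 = 6.7% | 2/16 = 12.5% | 5.8 points |

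**Step 4. Table trigger.** If four Safety Set subjects have an AE and one more is excluded, the count is 4 and no AE summary table is produced. With that subject included it is 5 and the tables appear.

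**Step 5. Direction.** The downward bias needs the excluded subject to have had an AE. If the excluded subject had none, the reported rate rises slightly: with e = 4, 4/49 = 8.2% against 4/50 = 8.0%.

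**The case against.** **The strict reading is not forced.** The rule does not say entire or complete contents, and its clause about unfinished HF assessments suggests an inclusive intent. A programmer could admit part-capsule subjects. This stands as far as it goes, but membership would then be settled by interpretation once data exist.

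**Few subjects would be caught.** Protocol 13.4.5 says most users can empty a capsule in one inhalation, so many who react to the first breath would still qualify. This stands and limits the size.

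**Stronger readings that the documents do not support:**

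- *Subjects who used all four capsules but left residue in each would also be dropped.* Residue is judged by the HF Interviewer and kept as HF data, which SAP Section 1 places outside the clinical database. The 14 of 45 patients in the earlier IFU study (Protocol 13.5.2) did not empty all four capsules. The summary does not report anyone who failed to empty even one.
- *The events disappear entirely.* CRF recording and SAE reporting continue, and the restriction of listings is an inference from a general note. The gap is in planned outputs.
- *Replacement fills the place with someone who tolerated the powder.* Protocol 5.6.2 replaces by age category, not by tolerance, and replacements can have AEs that are counted.
- *The report could show 0/45 when the truth is 5/50.* That needs all five implied non-completers to react and stop within capsule 1, with no AE in anyone else. Nothing in the documents points to that.

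**The data are secondary.** SAP Section 2 calls the clinical data supplementary, and the primary assessment of use errors and close calls does not rest on the Safety Set. This stands.

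**Conclusion.** The point holds in a limited form. On the natural reading, a subject who reacts and is stopped partway through capsule 1 is exposed but outside both analysis sets, so the AE is missing from the AE, AE-withdrawal and disposition tables. Whether it also leaves the listings depends on how the SAP 2.2 note is applied.

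For such subjects the tabulated AE rate is biased downwards, by about 2 points overall and about 6 points in an age group of 16 per excluded case. These sizes assume 50 exposed subjects, or 16 in the age group, and an excluded subject who had an AE. How many there would be is unknown and probably small. The sample size, the primary assessment and safety surveillance are unaffected. Because the rule can select on the outcome and is easily corrected, it should be changed rather than left to interpretation.

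**What to change.** In Protocol 9 and 9.1 and SAP 2.1 and 2.2, define the Safety Set as all enrolled subjects who started inhalation from a loaded capsule, regardless of powder remaining or completion of the HF assessment. In SAP 2.5.1, state that AE and SAE listings cover all enrolled subjects. If only the SAP is changed, record the departure in SAP Section 4, which now reports none.

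**Data needed.** Protocol 5.5.1 already requires the IRT to be told when a patient does not start inhaling, so start-of-inhalation status is tracked without HF records. The SAP summarises clinical-database data, so that status must be reconciled into the database, or a single eCRF field added if it is not there.

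**Cost.** Mainly a wording change. A subject who inhaled from an unpierced capsule may be counted as exposed, which adds slightly to the denominator.
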